2.7.3 Handling of missing values/censoring/discontinuations

For patients who prematurely discontinue the study for any reason or patients with missing visits (after baseline), PASI will be imputed using the Last Observation Carried Forward

Novartis	For business use only	Page 28
SAP Amendment 2.0		AIN457AIT01

(LOCF) approach. If all PASI post-baseline efficacy values are missing, then these missing values will not be imputed and this patient will be removed from the analysis.

A multiple imputation approach on continuous PASI will be also taken into account. If all PASI post-baseline efficacy values are missing, then these missing values will not be imputed and this patient will be removed from the analysis.

2.8 Safety analyses

All the safety analysis will be performed on Safety set by study phase (i.e. CORE and Extensions) and overall.

2.8.1 Adverse events (AEs)

A summary table of AEs will be produced by cohort specifying the number of total events and the absolute and relative frequency of patients with AEs. All AEs which occur on or after the first dose of study treatment and on or before last dose of treatment will be considered as treatment emergent and remaining will be considered as non-treatment emergent. AEs which occur till last visit date of E0 will be reported under Core phase and which start after E0 visit will be reported under Extension phase. The detailed treatment emergent rules for AE reporting by phases are mentioned below:

Core phase

AEs occurring on or after first dose date and

- a) on or before the last visit date till E0, if patient discontinued the study
- b) on or before the last dose date till E0, if patient completed the study

Extension phase

- 1) Patient entered and dosed in extension
- 2) AEs occurring on or after first dose in extension and
 - a) on or before last visit date, if patient discontinued the Extension phase study
 - b) on or before last dose date, if patient completed the Extension phase study

Overall:

AEs occurring on or after first dose date and

- a) on or before last visit date if patient discontinued the Core or Extension phase study
- b) on or before last dose date if patient completed the study

Note: In addition to that, if last visit date is missing and last dose is after the non-missing last visit date, then treatment emergent flag will be considered till the last dose date.

The absolute and relative frequency of patients with study drug related AEs, SAEs, AEs with an outcome of death (if data is sufficient), AEs leading to discontinuation of treatment will be also reported by cohort and overall. Proportion and 95% CI will be calculated using exact binomial method. Differences between cohorts will be assessed by means of a logistic model

with factors (time of exposure, age at baseline (tertiles), sex, number of comorbidities (General and PsA), BMI class). Tertiles will be calculated from SAS using PROC Univariate of age at baseline.

AEs will be tabulated also by System Organ Class, Preferred Term. SAEs will be summarized as well. All study drug related AEs, AEs with an outcome of death, AEs leading to discontinuation of treatment will be listed. The above reported analysis will focus on treatment emergent adverse events.

A treatment-emergent adverse event is defined as any adverse event that develops after initiation of the study treatments or any event already present that worsens following exposure to the study treatment.

Non-treatment emergent adverse events will be listed separately.

Additionally, differences between cohorts in total number of AEs / SAEs/ AEs of special interest, by study period and overall, will be done with a poisson regression model adjusting over time of exposure, age at baseline (tertile), sex, number of comorbidities and BMI class.

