• For the subjects who did not enter Extension Phase, all events/medications belongs to Core Phase

- · If event/medications start date is on or before visit date of E0, then APERIOD=Core Phase
- If event/medications start date is after visit date of E0, then APERIOD=Extension Phase.

For Planned data (i.e., Visit wise, all safety and efficacy) will be derived as below:

- · Visits before E0 will belong to Core Phase
- · Visits on or after E0 will belong to Extension Phase

Basically reporting will be done for visit assessment data in extension phase which is collected on or after ICF is signed for extension phase.

The above rules are irrespective of whether V12 visit date and E0 visit date are same or different.

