2.1.1.6 Visit windows

Visit windows will be used for the data that is summarized by visit. They are based on the study evaluation schedule and comprise a set of days around the nominal visit day. For any assessment, there are the protocol defined scheduled visits around which visit windows were created to cover the complete range of days within the study. The visit windows in this study are shown in the below Table 2.1, the days are counted since the first dose of study treatment. These visit windows apply to measurements taken at every visit. When visit windows are used, all visits will be re-aligned, i.e., they will be mapped into one of the visit windows. E.g., if the Week 4 visit of a patient is delayed and occurs on Day 46 instead of on Day 28, say, it will be re-aligned to visit window Week 8. If two visits fall into one window then the visit closest to target scheduled day will be analysed for that visit.

Visit	Week	Scheduled day	Visit Window
Screening (Visit1, Visit2)	-4	-28	-28 Days to Day -4
Baseline (Visit 3)	0	1	-3 day to Day 1
Visit 4	1	7	Day 2-10
Visit 5	2	14	Day 11-17
Visit 6	3	21	Day 18-24
Visit 7	4	28	Day 25-42
Visit 8	8	56	Day 43-70
Visit 9	12	84	Day 71-98
Visit 10	16	112	Day 99-126
Visit 11	20	140	Day 127-154
Visit 12	24	168	Day 155-210
E1	36	252	Day 211-294
E2	48	336	Day 295-378
E3	60	420	Day 379-462
E4	72	504	≥ 463 Day

Table 2.1	Assessment windows	for scheduled visits
-----------	--------------------	----------------------

Case 1) If V12 and E0 visit dates are same then:

Visit	Wk	Day	Window
V12	24	168	Day 155-210
E1	36	252	Day 211-294
E2	48	336	Day 295-378
E3	60	420	Day 379-462
E4	72	504	≥ 463 Day

Case 2) If	V12	and	E0	dates	are	different	then:

Visit	Wk	Day	Window
V12	24	168	Day 155-(A(E0)-1)
E0	24	A(E0)	A(E0) – (A(E0) +42)
E1	36	(A(E0) +43)+41	Day (A(E0) +43) – (A(E0) +43+83)
E2	48	(A(E0) +43+84)+41	Day (A(E0) +43+84) – (A(E0) +43+2*83)
E3	60	(A(E0) +43+2*83+1)+41	Day (A(E0) +43+2*83+1) – (A(E0) +43+3*83)
E4	72	(A(E0) +43+3*83+1)+41	> Day (A(E0) +43+3*83)

Where A(E0) date implies Actual Visit date of E0.

Note if A(E0) date = Day 168, which is the theoretical study day of V12, then both the table gives same windows.

If E0 is not assessed, then combine the window of E0 and E1 for E1 visit, i.e., E1 window will start from E0. Target day of E1 will remain same.

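### SAP 2.8.1 assigns post-E0 adverse events to the extension, but its detailed treatment-emergent rules open the extension window at an undefined first dose and can leave up to about four weeks in neither phase

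*SAP*

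**What the plan says.** SAP 2.8 asks for all safety analyses by study phase and overall. Two general statements split AEs at E0:

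- The lead-in of SAP 2.8.1 reports events up to E0 under core and says that those "which start after E0 visit will be reported under Extension phase".
- SAP 2.1.1.5, for spontaneous data, puts events on or before the E0 date in core. Its rule for later events ends "visit date of E0, then APERIOD=Extension Phase". It adds: "The above rules are irrespective of whether V12 visit date and E0 visit date are same or different".

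SAP 2.8.1 then gives detailed treatment-emergent rules by phase:

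- **Core, rule a:** "on or before the last visit date till E0, if patient discontinued the study".
- **Core, rule b:** "on or before the last dose date till E0, if patient completed the study".
- **Extension, rule 1:** "Patient entered and dosed in extension".
- **Extension, rule 2:** "AEs occurring on or after first dose in extension and" then an end date, which is the last visit (discontinued) or last dose (completed).

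The overall window runs unbroken from the first study dose.

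On dosing, Protocol 5.5.4 and Table 6-1 schedule the week-24 dose at visit 12 of the core study. Extension doses are self-administered every 4 weeks for 48 weeks. Table 6-2 has drug dispensed for home use at E0 and lists administration only as needed. Its footnote makes E0 the same visit as week 24, but SAP 2.1.1.6 also provides (Case 2) for V12 and E0 on different dates, with windows keyed to the actual date: "Where A(E0) date implies Actual Visit date of E0".

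**The concern.** The general statements say which phase an event belongs to. The detailed rules say whether it is treatment-emergent in that phase, and 2.8.1 states that its AE analysis focuses on treatment-emergent events. An event can therefore be assigned to the extension and be treatment-emergent overall, yet fail the extension's treatment-emergent rule because it started before the first extension dose. The start of that window depends on a term that is not defined.

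What is at stake is the by-phase safety output: the treatment-emergent tables, the special-interest summaries and the logistic and Poisson models. Long-term safety is one of the three stated purposes of the extension. Two programmers working from the same text could produce different extension tables. On one reading, core plus extension would not add up to overall. Rule 1 could also remove from the extension set a patient who enters, has an event and stops before the first home dose.

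**Working it through.** The documents state no gap length, so there is no figure of theirs to reproduce.

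**Inputs**

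- Visits 8 to 12 fall on Days 56, 84, 112, 140 and 168 (Protocol Table 6-1), so the dosing interval is 28 days.
- V12 and E0 are nominally on Day 168 (SAP 2.1.1.6), with ±7 days allowed (Protocol Tables 6-1 and 6-2).
- First home dose: 168 + 28 = Day 196. This is inferred from the 4-weekly schedule and is stated nowhere.
- E4 is on Day 504, so the extension lasts 504 − 168 = 336 days.
- Planned extension patients: 306 (Protocol section 4).

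**Formula**

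Gap = (first extension dose day) − (core window end day) − 1, or zero if that is negative.

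| Case | Core ends | Extension opens | Days in neither phase |
|---|---|---|---|
| V12 = E0 = 168; week-24 dose is core | 168 | 196 | 196 − 168 − 1 = 27 (Days 169–195) |
| V12 = E0 = 168; E0-date dose is first extension dose | 168 | 168 | 0 |
| V12 = 168, E0 = 175; core rule b | 168 | 196 | 196 − 168 − 1 = 27 |
| V12 = 168, E0 = 175; core rule a | 175 | 196 | 196 − 175 − 1 = 20 |

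In the second row, Day 168 meets both treatment-emergent windows. The period rule in SAP 2.1.1.5 puts an event on the E0 date in core, so it is counted once.

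In the last two rows the scheduled week-24 dose is given at V12, before E0. Counting a dose on the E0 date as the first extension dose therefore does not help, because none is scheduled then. Of the 27 days under rule b, the general rule would give 7 (Days 169–175) to core and 20 (Days 176–195) to the extension.

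**Size in the first case**

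- Share of the extension: 27 / 336 = 8.0%.
- Patient-time: 306 × 27 = 8,262 patient-days; 8,262 / 365.25 = 22.6 patient-years.

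**Check of the remedy**

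If core ends at E0 and the extension covers events starting after E0, the gap is (E0 + 1) − E0 − 1 = 0 for E0 on Day 161, 168 or 175. No day falls in both windows.

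**The case against.** The strongest reply is that the SAP already settles the matter. Section 2.1.1.5 gives every event one period, split at E0. For planned visit data it places visits on or after E0 in the extension, and SAP 2.4.1 counts extension exposure from E0 to E4. On those conventions a dose on the E0 date is the first extension dose, and with V12 on the same day the gap is zero. This stands as a legitimate reading, and it is why 27 days cannot be presented as the only result.

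It does not remove the inconsistency. The period rule does not make an event treatment-emergent; 2.8.1 has its own rules for that, and they refer to dosing in the extension. Protocol 5.5.4 schedules the week-24 dose at a core visit, which makes it more natural to treat that dose as core. The zero-gap reading also depends on V12 and E0 sharing a date, and the SAP provides for the case where they do not.

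A second reply is that the date of the first home dose is unknown. That is correct. Every non-zero figure above rests on the inferred Day 196, and the documents do not say how often V12 and E0 differ.

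**Conclusion.** SAP 2.8.1 is internally inconsistent, and the start of the extension treatment-emergent window is undefined. The days left out of both phases range from 0 (E0-date dose counted as extension, V12 = E0) to 27 (week-24 dose counted as core). When V12 precedes E0, about 20 to 27 days can remain, depending on the core rule. The non-zero figures assume nominal visit days (E0 on Day 175 in the last case) and a first home dose on Day 196. The point is minor.

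Stronger conclusions that a reader might draw are not supported:

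- **That AEs are lost from the report.** The overall treatment-emergent window has no break and the listings remain. Only by-phase output is affected.
- **That E0-day events are counted twice.** The period rule assigns them to core alone.
- **That the cohort comparison or the primary result is biased.** The rule is the same for both cohorts, and the primary analysis is of PASI 90 at week 16.
- **That a known number of events would be missing.** Applying the 236.1 AEs per 100 patient-years in Protocol 3.6 to 22.6 patient-years would give about 53 (22.6 × 2.361). That pooled rate covers the entire treatment period in other trials. Nothing shows that it fits patients already responding at week 24.

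**What to change.** Edit SAP 2.8.1 only:

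1. **Core phase:** add that, for patients who enter the extension, the core treatment-emergent window ends at the E0 visit date.
2. **Extension rule 1:** replace the requirement to have been dosed with *Patient entered the extension*.
3. **Extension rule 2:** change the start to *AEs starting after the E0 visit date*, and keep end rules a) and b).
4. **Extension AE models:** where they adjust for time of exposure, use the same after-E0 window.

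This carries the SAP's own general rule into the detailed rules and works whether or not V12 and E0 share a date. The exposure and compliance text in SAP 2.4.1 can stay as it is: declaring the week-24 dose to be core only would conflict with its E0-to-E4 wording and is not needed.

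The cost is a few lines of SAP text and a small change to how events are flagged. No protocol amendment or new data are required, because AE start dates and E0 visit dates are already used by the SAP's own period rules.

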Section 2.2 Analysis sets

Analysis Sets added for clarity or additional analyses:

- All patients: all patients who signed informed consent and entered in the study, including screen failure.
- Core phase completers set: All patients who completed the Core phase visits (Week 24) are called core phase completer set.

Analysis Sets updated/ clarified (in bold):

- Safety: all enrolled patients **included in the FAS population** who were given at least one dose of study drug.
- Intent-to-treat (ITT): all patients included in the safety population with at least one post-baseline efficacy assessment and with the Cw6 assessment.

Section 2.3.1:

By visit disposition summary table is added.

Section 2.3.2:

P-values of comparison of cohorts will be analysed based on stratified CMH, and logistic model with covariates (for categorical variables) and ANCOVA (for continuous variables).

Total number of comorbidities (all medical histories) between cohorts will be analyzed by Poisson model adjusted by covariates.

Section 2.4.2:

Previous psoriasis therapies will be analysed by logistic model and total number of such therapies will be analysed by Poisson model after adjusting for covariates.

Section 2.5:

The model factors are clarified in the SAP.

Non-responder imputation is added. Analyses based on NRI for primary and secondary efficacy endpoints are added.

Modelling approaches of PASI scores and IGA scores have been included based on MMRM. Modelling of IGA0/1 responder is also added.

Section 2.8.1

The AEs comparison of cohorts will be done based on CI and pvalues generated from logistic model or poisson model (for total number of events overall).

The AESI of RMP related events will be summarized and compared based on logistic model approach.

Section 2.8.4

ANCOVA model for vital signs are added.

5 Appendix

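### SAP 2.8.1 closes the treatment-emergent AE window in two conflicting ways; separately, the notable-haemoglobin criterion cannot be met from any baseline below 20 g/dL

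*SAP*

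**What the plan says.** SAP 2.8.1 opens with a general sentence: AEs that occur from the first dose and "on or before last dose of treatment will be considered as treatment emergent and remaining will be considered as non-treatment emergent". It then sets out detailed rules by phase and overall. The Overall window closes "on or before last visit date if patient discontinued the Core or Extension phase study", but "on or before last dose date if patient completed the study". The core and extension rules split patients in the same way.

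For a patient who completes, the core window ends "on or before the last dose date till E0, if patient completed the study". The extension item begins "AEs occurring on or after first dose in extension and" and then gives the same two closing dates. AEs "which start after E0 visit will be reported under Extension phase", in line with the period rule in SAP 2.1.1.5.

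The section also carries a definition with no end date: "A treatment-emergent adverse event is defined as any adverse event that develops after initiation of the study treatments", or that worsens after exposure. Protocol 9.5.2 has the same definition. For 2.8.1, SAP section 4 records only added models, for example: "The AEs comparison of cohorts will be done based on CI and pvalues generated from logistic model or poisson model".

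The text of SAP 2.8.1 and 2.8.1.1 adjusts the Poisson comparisons for time of exposure. The sample Poisson code in SAP 5.4.3 has cohort, age group and sex only.

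Protocol Appendix 1 and SAP Table 2.8.3 both define a notable haemoglobin value as a decrease from baseline of 20 g/dL or more.

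**The concern.** The two closing rules give different answers for the same event. Reported AE analyses focus on treatment-emergent events and the rest are only listed, so two programmers could produce different tables and different inputs to the cohort models.

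The events most exposed are those around stopping. Dosing is every 4 weeks after induction. An AE that starts between doses and leads the patient to stop has its onset after the last dose by construction. The general sentence removes it from the emergent tables; the rule for discontinued patients keeps it if it starts by the last visit.

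Comparing safety between cohorts to week 72 is a secondary objective, and SAP 2.8 asks for safety by phase and overall, so those tables should reconcile. If the core and extension windows do not meet, an AE can be emergent overall and in neither phase.

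The haemoglobin row is a separate fault in a laboratory table: a criterion that nobody can meet gives an empty row that may be read as reassurance.

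**Working it through.** The plan derives none of these figures, so there is nothing to reproduce. The check compares the rules and does day arithmetic on the schedule.

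**Inputs.** Scheduled days (protocol Table 6-1, SAP Table 2.1): week 12 = day 84, week 16 = 112, week 20 = 140, week 24/E0 = 168, week 72/E4 = 504. Week 68 = 68 × 7 = day 476. Doses every 4 weeks through visit 12, then every 4 weeks for 48 weeks (protocol 5.5.4). Patients who stop treatment are asked to keep attending (protocol section 6). Planned enrolment is 406, with 306 in the extension (protocol section 4).

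**1. Closing rules, for an AE after the last dose and by the last visit**

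| Patient | General sentence | Detailed rules | Open-ended definition |
|---|---|---|---|
| Discontinued | not emergent | emergent | emergent |
| Completed | not emergent | not emergent | emergent |

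For discontinued patients, days in dispute = last visit − last dose:
- Last dose day 84: 112 − 84 = 28, 140 − 84 = 56, 168 − 84 = 84.
- Last dose day 112: 0, 28 and 56 for the same three last visits.

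For completers the two rules agree, but the detailed rules close their window at the last dose, while a discontinued patient's runs to the last visit. The part of a completer's follow-up cut off in this way is:
- Core only: 168 − 168 = 0 days.
- Extension: 504 − 476 = 28 days (28/504 = 5.6%) if the last dose is at week 68; 0 if at week 72.

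The note that follows the detailed rules does not settle the matter, because it describes the last visit date as both missing and non-missing.

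**2. Where the phases meet**
- Week-24 dose closes the core and also counts as the first extension dose: no gap.
- Week-24 dose is a core dose and the first extension dose is at week 28 (168 + 28 = day 196): days 169 to 195 fall in neither phase window, which is 27 days (27/336 = 8.0% of the extension). They are still inside the Overall window.

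**3. The 27 and 28 days are largely alternatives.** Every 4 weeks for 48 weeks, read as 48/4 = 12 doses:
- First dose at week 28: last at 28 + 11 × 4 = week 72. Gap 27 days, completer cut-off 0.
- First dose at week 24: last at 24 + 11 × 4 = week 68. Gap 0, completer cut-off 28 days.

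**4. Poisson code run exactly as printed.** Assume equal true AE rates and follow-up of 168 days without the extension and 504 with it. Mean follow-up = 168 + 336p, where p is the proportion entering the extension; the average is 306/406 = 0.754.
- No difference in p between cohorts: ratio 1.00.
- 5 points (0.779 v 0.729): 429.6/412.8 = 1.04.
- 10 points (0.804 v 0.704): 438.0/404.4 = 1.08.

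**5. Haemoglobin.** Decrease = baseline − post, and post cannot be below 0, so the decrease cannot exceed the baseline. Baselines of 10, 12, 15, 18 and 19.9 g/dL would need post values of −10, −8, −5, −2 and −0.1 g/dL. The protocol's exclusion limit for haemoglobin (below 10 g/dL) is in the same unit.

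**The case against.** **The detailed rules are introduced as the ones for reporting, so a programmer would probably follow them.** That is likely, but the general sentence makes every remaining AE non-emergent, so it cannot be read as a summary of the detailed rules. The unequal treatment of completers and discontinued patients remains in either case.

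**A reader might count three conflicting closing rules.** The documents do not support that. The definition in SAP 2.8.1 and protocol 9.5.2 has no closing date. It fails to settle the conflict but is not a third rule. Nor is the lack of a section 4 entry a fault in itself, since protocol section 9 leaves analysis detail to the SAP.

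**A reader might take the 27-day gap as established** and multiply it up to 306 × 27 = 8,262 patient-days. That applies the less supported reading to every patient. SAP 2.4.1 presents extension exposure from E0 to E4, and the core rule runs up to E0, which favours no gap. It is not conclusive, because SAP 2.4.1 also takes core exposure up to week 24, and protocol Table 6-2 shows dispensing at E0 without saying when the first home dose is taken.

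**A reader might infer that the Poisson comparison ignores follow-up.** The text requires adjustment for time of exposure. The printed code also lacks BMI class and comorbidities and splits age at 40 instead of by tertiles, so it is a template. What stands is narrower: the code does not match the text, and if time of exposure means first to last dose (SAP 2.4.1), it does not cover a discontinued patient's window to the last visit.

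**A reader might infer that a window to 30 days after the last visit matches data collection.** The 30-day rule in protocol 7.2 covers serious AEs only. Protocol 7.1 leaves later non-serious AEs in source documents, and SAP 5.1.1 caps imputed AE end dates at the completion or discontinuation visit. Complete capture of non-serious AEs to 30 days is not shown.

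**Conclusion.** Two faults are firm. SAP 2.8.1 contradicts itself on when the treatment-emergent window closes for patients who discontinued, and its detailed rules give them a different window from completers. The notable-haemoglobin criterion cannot be met from any baseline below 20 g/dL, so in practice the row will flag nobody.

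The size of the first depends on how many patients stop early and keep attending, which the documents do not give; 28 to 84 days per patient is an on-schedule illustration for a last dose at week 12. The phase gap is 0 days on the reading that SAP 2.4.1 favours and up to 27 on the other. It should not be added to the 28-day cut-off for extension completers.

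A biased cohort comparison does not follow from this alone. It would need discontinuation or follow-up to differ by Cw6 status, and its size and direction are unknown. The ratios of 1.04 and 1.08 are illustrations that hold only if the printed code is run unchanged and extension entry differs by Cw6. Extension entry depends on PASI 75 at week 24, but protocol 1.1 expects no difference in efficacy.

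A slip of unit in the haemoglobin criterion is a natural guess, but neither document says so. Falls in haemoglobin still appear in the change-from-baseline summaries, shift tables and high/low listings. The primary PASI 90 analysis is not touched.

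**What to change.** 1. State one closing rule for all patients, whatever their completion status, and delete the conflicting sentence. The last study visit would serve. A later date should be used only if the sponsor confirms that non-serious AEs are captured on the CRF up to that date.
2. For phase tables of continuing patients, end the core window on the E0 date and start the extension window the next day, as SAP 2.1.1.5 already assigns AEs. Each day then belongs to one phase, however the week-24 dose is counted.
3. Minor: bring the sample Poisson code into line with the text by including follow-up time over the same window as the events counted, for example its logarithm as an offset, kept apart from drug exposure as defined in SAP 2.4.1.
4. Have the sponsor confirm the intended haemoglobin value and unit, and correct protocol Appendix 1 and SAP Table 2.8.3 together.

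The cost is SAP wording, reprogramming of the treatment-emergent flag, one follow-up variable and one entry in each of two tables. Treatment-emergent counts may rise slightly. Closing at the last visit needs no new data.
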